### **5.1.3 Specimen Collection:** Tissue specimens should be taken from pre-study diagnostic open biopsy or surgical resection.

**5.1.3.1** To be eligible for this study, the patient must have an ependymoma. Features of a grade II or III ependymoma according to WHO guidelines must be present.

**5.1.3.2** The following materials will be required for tissue evaluation:

5.1.3.2.1 Representative tissue blocks that contain diagnostic tumor. As a guide, at least 1 cubic centimeter of tissue composed primarily of tumor is desired. If tissue block is not available, 15 unstained slides from a representative tumor block is required.

5.1.3.2.2 If a representative tissue block is submitted, an accompanying H&E is encouraged for rapid diagnosis but not required. If an H&E is included, [name] will use this for the review. If not included, [name] will cut a section from the paraffin block, stain this with H&E, and use that slide for the review.

5.1.3.2.3 A Pathology Report documenting that the submitted material contains tumor; the report must include the protocol number, patient case number, and the patient's initials. The patient's name and/or other identifying information should be removed from the report. The surgical pathology numbers and information must NOT be removed from the report.

5.1.3.2.4 Tissue evaluation will be required for every case before study registration Step 2. Send pathology material by overnight mail directly to:

[name]  
MacFeeters- Hamilton Centre for Neuro-Oncology,  
[name]  
Princess Margaret Cancer Centre,  
Toronto Medical Discovery Tower (TMDT),  
[name]  
Canada  
[[contact]](mailto:[contact])

- 5.1.3.2.5 Include on the tissue submission form the name, telephone number, and fax number of the person to notify with the results of the tissue evaluation.
- 5.1.3.2.6 Shipments must be made Monday through Thursday.
- 5.1.3.2.7 Notify [name] by email on or before the day of submission: (1) that a case is being submitted for review; (2) the name of the contact person; (3) when to expect the sample; and (4) the overnight shipping carrier and tracking number.
- 5.1.3.2.8 [name] will email the appropriate contact person from the submitting institution with the results and will send the completed form to the institution electronically.
- 5.1.3.2.9 If the patient does not meet eligibility requirements, *all* tissue and forms will be returned to the participating submitting institution.
- 5.1.3.2.10 If a tissue block is provided, after confirming histopathologic diagnosis [name] will cut sections for molecular analysis.

## **5.2 LABORATORY CORRELATES**

Relative to other gliomas, little is known regarding the relevant molecular lesions in ependymoma that contribute to the biologic and clinical behavior of these neoplasms. Activation of the EGFR pathway, as stated above, has been described. In addition, while MGMT methylation has been reported at low frequency, too few cases have been evaluated to lead to firm conclusions. Finally, activation of the PI3K-AKT pathway has not been fully characterized, and its evaluation is justified based on the central role of this pathway in human tumors. Accordingly, molecular testing will include an evaluation of these pathways as well as genome wide screens. Tumor tissue will be evaluated immunohistochemically for expression of EGFR. Activation of the PI3K/AKT pathway will be determined by immunohistochemistry for p-AKT, p-mTOR as well as p-S6. MGMT methylation will be determined using real-time PCR of DNA following bisulfite treatment. Since little is known regarding molecular lesions in ependymoma, genome-wide screens will be performed and will include microarray expression profiling using the Illumina DASL assay (unpublished data from our laboratory suggest that this is feasible in formalin-fixed paraffin embedded tissue). Data from the Cancer Genome Atlas indicate that methylation profiling in glioblastoma is likely to lead to clinically useful biomarkers. Accordingly, methylation profiling using the Illumina Golden Gate Cancer panel, will be performed on these ependymoma samples. These screens as well as the targeted molecular assays will provide the basis for a future molecular classification of ependymoma based on site of origin as well as clinical factors (grade and patient outcome).

## **6 DATA COLLECTION AND EVALUATION**

### **6.1 DATA COLLECTION**

Data will be collected/reported in a secure research database. The PI will be responsible for overseeing entry of data and ensuring data accuracy, consistency and timeliness. The principal investigator, associate investigators/research nurses and/or a contracted data manager will assist with the data management efforts. All data obtained during the conduct of the protocol will be kept in secure network drives or in approved alternative sites that comply with NIH security standards. Primary and final analyzed data will have identifiers so that research data can be attributed to an individual human subject participant.

Sites will enter data on paper Case Report Forms; then transfer study data to NCI via fax, mail or Secure E-mail and File Transfer Service (SEFT). Contracted Data Managers will enter the data into a secure research database.

**End of study procedures:** Data will be stored according to HHS, FDA regulations and NIH Intramural Records Retention Schedule as applicable.

**Loss or destruction of data:** Should we become aware that a major breach in our plan to protect subject confidentiality and trial data has occurred, the IRB will be notified.

#### 6.1.1 Confidentiality

All documents, investigative reports, or information relating to the patient are strictly confidential. Any patient specific reports (i.e., Pathology Reports, MRI Reports, Operative Reports, etc.) submitted to the NCI must have the patient's full name & social security number "blacked out" and the assigned patient ID number, protocol accession number, and protocol number written in. Patient initials may be included or retained for cross verification of identification.

#### 6.1.2 Certificate of Confidentiality

As part of study efforts to provide confidentiality of subject information, this study has obtained a Certificate of Confidentiality, which helps to protect personally identifiable research information. The Certificate of Confidentiality allows investigators on this trial to refuse to disclose identifying information related to the research participants, should such disclosure have adverse consequences for subjects or damage their financial standing, employability, insurability or reputation. The informed consent includes the appropriate coverage and restrictions of the Certificate of Confidentiality.

#### 6.1.3 Safety Data

All patients receiving study agents will be evaluated for safety. The safety parameters include all laboratory tests and hematological abnormalities, CNS observations, physical examination findings, and spontaneous reports of adverse events reported to the investigator by patients. All toxicities encountered during the study will be evaluated according to the NCI Common Terminology Criteria for Adverse Events (CTCAE) version 4.0 and recorded prior to each course of therapy. Life-threatening toxicities that are unexpected and assessed to be possibly related to the study agent/s should be reported immediately to the study Coordinator and Institutional Review Board (IRB).

Information about all adverse events, whether volunteered by the subject, discovered by investigator questioning, or detected through physical examination, laboratory test or other means, will be collected and recorded on the Adverse Event Case Report Form and followed as appropriate. An adverse event is any undesirable sign, symptom or medical condition occurring

after starting study drug (or therapy) even if the event is not considered to be related to study drug.

Medical conditions/diseases present before starting study treatment are only considered adverse events if they worsen after starting study treatment (any procedures specified in the protocol). Adverse events occurring before starting study treatment but after signing the informed consent form are recorded on the Baseline Evaluations Adverse Events Case Report Form. Abnormal laboratory values or test results constitute adverse events only if they induce clinical signs or symptoms or require therapy, and are also recorded on the Adverse Events Case Report Form.

## **6.2 RESPONSE CRITERIA**

6.2.1 The primary endpoint is median progression-free survival. A combination of the neurological examination and MRI brain scan will be used to define progression. Due to improvements in neuroimaging and the fact that tumor growth in certain regions of the CNS is without immediate neurologic signs and symptoms, greater reliance is placed on neuroimaging to define progression.

6.2.2 Definitions of Response

6.2.2.1 **Measurable Disease:** Bi-dimensionally measurable lesions with clearly defined margins by MRI scan.

6.2.2.2 **Objective Status, To Be Recorded at Each Evaluation:** If there are too many measurable lesions to measure at each evaluation, choose the largest two to be followed before a patient is entered on study. The remaining lesions will be considered evaluable for the purpose of objective status determination. Unless progression is observed, objective status can only be determined when ALL measurable and evaluable sites and lesions are assessed.

6.2.3 Response Criteria

6.2.3.1 **Stable/No Progression:** No evidence of new measurable lesions on MR imaging. The designation of Stable/No Progression requires a minimum of 12 weeks duration. All measurable and evaluable sites must be assessed using the same techniques as baseline.

6.2.3.2 **Partial response:**  $\geq 50\%$  reduction in the sum of products of all measurable lesions over baseline sum observed using the same techniques as baseline. The patient must be on a stable or decreased dose of corticosteroids to be evaluable for response.

6.2.3.3 **Complete response:** Complete resolution of all lesions. The patient cannot be on any corticosteroids with the exception of adrenal replacement doses.

6.2.3.4 **Progression:** 25% increase in the sum of products of all measurable lesions over smallest sum observed (over baseline if no decrease) using the same techniques as baseline, OR clear worsening of any evaluable disease, OR appearance of any new lesion/site, OR failure to return for evaluation due to death or deteriorating condition (unless clearly unrelated to this cancer).

6.2.3.5 **Unknown:** Progression has not been documented and one or more measurable or evaluable sites have not been assessed.

6.2.4 **Neurologic Function Score:** This method of neurologic evaluation notes the presence or absence of neurologic symptoms. This examination should coincide with objective measurement in tumor size.

0	No neurologic symptoms
1	Minor neurologic symptoms
2	Moderate neurologic symptoms – fully active
3	Moderate neurologic symptoms – less than fully active
4	Severe neurologic symptoms

- 6.2.5 **Performance Status:** Patients will be graded according to Karnofsky Performance Status (KPS)
- 6.2.6 **Time to Treatment Failure:** From date of registration to the date of first observation of progressive disease, non-reversible neurologic progression or permanently increased steroid requirement (applies to stable disease only), death due to any cause, or early discontinuation of treatment.
- 6.2.7 **Survival:** From date of registration to date of death due to any cause
- 6.2.8 **NOTE: Steroids:** Steroid dosage will be carefully monitored and recorded during each course of therapy and steroid dosage changes will be considered before response determinations are made.

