### **3.7 ON STUDY EVALUATION**

- 3.7.1 Physical Exam to include, Vital Signs, a neurologic examination, and KPS Performance status, will be performed every 8 weeks prior to initiation of every other cycle of therapy (i.e prior to cycle 3, cycle 5, cycle 7 etc.) and when therapy is discontinued. Patient treatment diaries will be collected and pill counts will be performed prior to every other cycle of therapy and when therapy is discontinued.
- 3.7.2 Total protein, albumin, calcium, phosphorus, glucose, BUN, creatinine, uric acid, alkaline phosphatase, LDH, and when appropriate, anticonvulsant levels will be performed prior to initiation of treatment and before each course of therapy.
- 3.7.3 MRIs will be done before every other course of treatment (prior to cycle 3, 5, 7. etc.).
- 3.7.4 MDASI-BT and/or SP at the time of clinical evaluation with MRI as long as the clinical therapy is being administered (Appendix 12.7 or 12.8).
- 3.7.5 A CBC with differential and platelets will be obtained every 2 weeks.
- 3.7.6 Hepatic Monitoring: SGPT (ALT), total bilirubin levels will be performed:
  - During treatment phase: every 4 weeks, prior to each course of therapy, for the duration of chemotherapy administration (or more frequently, if clinically indicated)
  - During post-treatment phase: continue to monitor any liver chemistry abnormalities noted during treatment or within 30 days after last dose of lapatinib until values return to normal or baseline
  - bilirubin fractionation (when testing is available) is recommended if total bilirubin >2 x ULN
  - See section 3.7.6 and Appendix 12.5 for Liver Chemistry Stopping and Follow-up criteria in the presence of abnormal LFT results.
- 3.7.7 Cardiac Monitoring:
  - LVEF will be assessed every 8 weeks (2 cycles) by Echo or MUGA (MUGA preference as clinically indicated) scan. The method of evaluation used for the

LVEF assessment in an individual subject must be the same method used at baseline and throughout the duration of the trial.

- Echo or MUGA (if clinically indicated) studies must be performed under the supervision of an experienced cardiologist, presumably at the same high-volume laboratory for the duration of the trial. The guidelines of the American Society of Echocardiography will be used. These guidelines can be located on the www at <http://www.asecho.org/Guidelines.php>
- Subsequent scheduled LVEF assessments must be performed as per Appendix 12.6, “LVEF Assessment Algorithm”.

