### Secondary Efficacy Analysis

The secondary endpoint of this trial is anti-tumor activity as determined by the overall response (CR or PR) rate. MacDonald criteria will be used to determine the overall response. Patients must have completed at least 4 weeks of treatment to be considered evaluable for overall response, unless treatment is stopped for neurologic progression. Patients with neurologic progression will be scored as non-responders regardless of duration of treatment.

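### Section 6.2.3 sets no confirming scan or minimum duration for PR or CR, and Section 8 names a second, unreconciled set of criteria for the response rate

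*Combined protocol and SAP*

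**What the plan says.** Section 6.2.3.2 grants a partial response for a 50% or greater "reduction in the sum of products of all measurable lesions over baseline sum observed using the same techniques as baseline", and adds: "The patient must be on a stable or decreased dose of corticosteroids to be evaluable for response". Section 6.2.3.3 reads: "Complete resolution of all lesions. The patient cannot be on any corticosteroids with the exception of adrenal replacement doses". Section 6.2.2.2 has objective status recorded at each evaluation. Neither response category carries a repeat scan or a minimum duration. Section 6.2.3.1, in the same list, does carry one for stable disease: "The designation of Stable/No Progression requires a minimum of 12 weeks duration".

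Section 8, Secondary Efficacy Analysis, makes response an endpoint: "The secondary endpoint of this trial is anti-tumor activity as determined by the overall response (CR or PR) rate". It then names its own source for the definition: "MacDonald criteria will be used to determine the overall response". Those criteria are not reproduced, and nothing connects them to 6.2.3. The only timing rule there is that a patient must normally have had 4 weeks of treatment to be evaluable.

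On scanning, Section 3.7.3 says: "MRIs will be done before every other course of treatment", that is, about every 8 weeks.

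**The concern.** A patient whose sum of products is at or below half of baseline at one evaluation, on an acceptable steroid dose, meets 6.2.3.2 whatever the next scan shows. With 8-weekly MRI, a PR at week 8 followed by progression at week 16 satisfies the text, while a patient stable at week 8 who progresses at week 16 need not meet the 12-week rule for stable disease. A patient who completes 24 cycles has 11 on-treatment scans (before cycles 3, 5, ..., 23) and one at the end, all compared with a single baseline reading. Best response can therefore be the most favourable of several noisy comparisons.

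There is no control arm in which the same error would appear. The natural comparator is the 20% response rate of the retrospective chemotherapy series cited in Section 1.2.2, which the protocol calls a benchmark. With at most 50 patients, one extra response moves the rate by at least 1/50 = 2 percentage points. The responder label is also used for the marker correlation (objective 1.1.2.3, which may alternatively use 12-month PFS) and for the MDASI comparison of responders with non-responders.

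**Working it through.** **No plan figure to reproduce.** The documents give no target, alpha, power or decision rule for the response rate, and no measurement error. What follows illustrates direction and range only.

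**Direction.** Every response that is still met at the next scan is also met at a first scan. The unconfirmed rate therefore cannot be lower than the confirmed one.

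**Does another section supply a confirmation rule?**
- The 4-week rule in Section 8 concerns time on treatment, not persistence of response.
- The word sustained (Précis, 3.1, 3.8.4.1) governs access to post-protocol lapatinib and is undefined.
- The steroid and same-technique conditions limit some bias, but not random reading error or brief shrinkage.
- The MacDonald criteria might supply a rule. The documents do not say.

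**Illustration of reading error (all inputs assumed).** One lesion; lognormal error with the given CV per diameter, independent between readings; six scans sharing one baseline; 15% of patients truly respond and are always counted.

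1. SD per log diameter: s = √ln(1+CV²). A product of two diameters has log SD √2·s, and its ratio to baseline has log SD 2s.
2. Chance that one scan shows a reduction of at least 50% when the true ratio to baseline is r: Φ[(ln 0.5 − ln r)/(2s)].
3. For an unchanged tumour (r = 1):
   - CV 5%: z = −0.693/0.100 = −6.9, effectively nil.
   - CV 10%: z = −0.693/0.1995 = −3.47, or 0.03%.
   - CV 15%: z = −0.693/0.298 = −2.32, or 1.0%.
4. Chance of at least one such scan among six, and of two consecutive ones, was simulated because the readings share a baseline:

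| True change | CV 10%: any / two consecutive | CV 15%: any / two consecutive |
|---|---|---|
| 0% | 0.15% / 0.01% | 4.7% / 0.5% |
| −20% | 4.3% / 0.4% | 20.8% / 4.6% |
| −30% | 17.3% / 3.4% | 38.8% / 12.7% |

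5. Reported rate = 15% + 85% × mean false-response chance.
   - Non-responders all unchanged, unconfirmed: 15 + 85 × 0.0015 = 15.1% (CV 10%); 15 + 85 × 0.047 = 19.0% (CV 15%).
   - Equal mix of 0%, −20% and −30%, CV 10%: the mean is (0.15 + 4.3 + 17.3)/3 = 7.3%, giving 21.2% unconfirmed against 16.1% confirmed.
   - Same mix, CV 15%: the mean is (4.7 + 20.8 + 38.8)/3 = 21.4%, giving 33.2% against 20.0%.
   - Same mix, CV 5%: 15.1% against 15.0%. At CV 20%: 44% against 25%.
   - Same mix with three scans: 18.9% against 15.6% (CV 10%) and 27.3% against 17.7% (CV 15%).
   - Same mix with two equal lesions and six scans: 16% (CV 10%) to 23% (CV 15%) unconfirmed.

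**Illustration of short-lived shrinkage.** If 10% to 30% of responses do not last to a second scan, an unconfirmed 20% becomes 0.20 × 0.9 = 18% to 0.20 × 0.7 = 14% confirmed. In 50 patients, 10 responders become 9 to 7.

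**The case against.** A reader might infer that the unconfirmed rule is the operative one, and that the trial's response rate is inflated to something like 21%-33%. The documents support neither step.

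On the first, no section says that one scan is enough; that is read from the silence of 6.2.3. The analysis section names the MacDonald criteria for this endpoint, and whether they require confirmation cannot be settled here. This objection stands. It does not clear the plan, however. If those criteria require confirmation, 6.2.3 differs from them; if they do not, the gap remains. Either way the reader cannot tell from the documents which rule will be applied.

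On the second, the upper figures depend on their assumptions. The mix in which two thirds of non-responders shrink by 20%-30% is favourable to the concern: all patients enter with progression or regrowth, and the cited median time to progression is 9.9 months. A single lesion is also favourable, since 6.2.3 sums all measurable lesions. The protocol's 25% progression rule takes patients off therapy and shortens the series of scans; applying it lowers the 33% to about 30%. Under that rule 71%-79% of the modelled non-responders at CV 10%, and 89%-93% at CV 15%, would be falsely called progressed within six scans, so the larger error rates are hard to square with a workable trial. These points stand, and they are why the size is given only as a range starting near zero.

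The contrast with stable disease is not an error in itself. A minimum duration for no change has its own purpose, because every patient starts there. It shows only that the list contains a duration rule and that response was left without one.

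**Conclusion.** The point holds in a limited form. The written definitions of PR and CR contain no confirmation or duration requirement, and the plan names a second, unreproduced set of criteria for the same rate. If 6.2.3 is what is applied, the rate can only be higher than a confirmed one. How much higher is unknown: from almost nothing (CV 5%), through at most about 4 points (CV 10%-15%, non-responders unchanged), to 6-18 points above an assumed 15% true rate if many non-responders shrink by 20%-30%. The CVs, the number of scans and lesions, the independence of readings and the mix are all assumptions.

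The effect is confined to a secondary endpoint without a decision rule and to the marker and MDASI analyses that use responder status. Median PFS and the stopping rule do not use PR or CR status. This is a cheap improvement, not a threat to the main conclusion.

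**What to change.** State in both 6.2.3 and Section 8 which single definition governs the response rate, reconciled with the MacDonald criteria that Section 8 names. Simply pointing Section 8 at the present 6.2.3 would not do: it would replace the named criteria with an unconfirmed rule.

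Count PR or CR as confirmed only if it is still met at the next scheduled MRI, with the same technique and the same steroid condition. Report the unconfirmed rate beside the confirmed one. The documents do not say how the cited 20% was defined, and giving both rates keeps the comparison possible either way. State which of the two labels the marker correlation and the MDASI comparison use.

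The cost is wording. The 8-weekly MRIs are already scheduled, so no scans are added, and closed accrual (Section 2.3) does not prevent an analysis rule from being fixed or both rates from being reported. The downside is that the confirmed rate may be slightly lower, and a patient whose only qualifying scan is the last one is not a confirmed responder.

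### The steroid condition for partial response is worded as an evaluability rule, so patients with raised steroids but no progression can drop out of the response-rate denominator

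*Combined protocol and SAP*

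**What the plan says.** Section 6.2.3.2 defines partial response by shrinkage of measurable lesions and then adds: "The patient must be on a stable or decreased dose of corticosteroids to be evaluable for response". The next item, complete response in 6.2.3.3, carries its own steroid condition in different terms: "The patient cannot be on any corticosteroids with the exception of adrenal replacement doses".

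Section 8, Secondary Efficacy Analysis, names the endpoint: "The secondary endpoint of this trial is anti-tumor activity as determined by the overall response (CR or PR) rate". It then sets the condition for entering the rate: "Patients must have completed at least 4 weeks of treatment to be considered evaluable for overall response, unless treatment is stopped for neurologic progression". It adds a safeguard: "Patients with neurologic progression will be scored as non-responders regardless of duration of treatment". Steroids are not mentioned there.

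Three other places bear on the point:

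- Progression (6.2.3.4) has no steroid condition. Besides lesion growth and new lesions, its definition includes "OR failure to return for evaluation due to death or deteriorating condition (unless clearly unrelated to this cancer").
- Time to treatment failure (6.2.6) counts as failures patients with "non-reversible neurologic progression or permanently increased steroid requirement (applies to stable disease only").
- Section 6.2.8 has steroid dose recorded in each course and taken into account before response is determined, but does not say how.

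Objective 1.1.2.1 places the response rate in patients with measurable disease.

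**The concern.** A condition for being scored a responder and a condition for being evaluable do different things to a proportion. Failing the first leaves the patient in the denominator as a non-responder. Failing the second removes the patient from both numerator and denominator. Section 6.2.3.2 uses the second kind of wording, and Section 8 uses the same term for membership of the response-rate population.

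If the wording is followed literally, the patients removed cannot be credited with a partial response while their steroids are raised, so their removal can only raise the reported rate. The protocol quotes a 20% response rate from a retrospective series (Section 1.2.2) and calls those data a benchmark. In a single-arm trial a reader is likely to set the observed rate beside that figure.

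The choice also reaches two other analyses that need a responder status for each patient: the marker correlations in 1.1.2.3, and the symptom comparison of responders with non-responders in Section 8. A patient called not evaluable has no status in either.

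**Working it through.** **Step 1. Which patients does the wording affect?** The documents state no figure that could be reproduced here, so the first check is to take each type of patient through the rules.

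| Patient | Rule that applies | In the denominator? |
|---|---|---|
| Neurologic progression, any steroid dose | Section 8 scores as non-responder whatever the treatment duration | Yes |
| Meets 6.2.3.4, any steroid dose | Progression; no steroid condition | Yes, subject to the 4-week rule |
| Stable, steroids not raised, at least 4 weeks of treatment | Section 8 evaluability met | Yes |
| Steroids raised, no progression, at least 4 weeks of treatment | 6.2.3.2 read literally: not evaluable; Section 8 silent | Not settled |

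Only the last row is open. The protocol itself recognises such patients, because 6.2.6 provides for a raised steroid requirement within stable disease. The 4-week rule does not settle their position: it is a necessary condition, and meeting it does not cancel a second evaluability condition stated elsewhere. The category Unknown (6.2.3.5) turns on unassessed sites, so it does not cover them either.

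**Step 2. How far could the rate move?** Inputs:

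- N = 50, the maximum sample size in Section 8. This is an upper limit for the response denominator, because 1.1.2.1 requires measurable disease while 2.1.1.11 does not require residual disease at entry.
- R = 10 responders, which is 20% of 50. The 20% comes from Section 1.2.2 and is used only for illustration.
- k = number of non-responders in the open row who are left out. The documents do not give it. Assumed range: 0 to 10.

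Rate with all patients kept = R/N = 10/50 = 20.0%.

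Rate with k left out = R/(N − k):

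- k = 1: 10/49 = 20.4%
- k = 5: 10/45 = 22.2%
- k = 10: 10/40 = 25.0%

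The increases are 0.4, 2.2 and 5.0 percentage points. With a smaller measurable-disease group, taken for illustration as N = 30 and R = 6:

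- k = 1: 6/29 = 20.7%
- k = 5: 6/25 = 24.0%
- k = 10: 6/20 = 30.0%

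**Step 3. Does it reach the primary analysis?** No. Section 8 builds time to progression, and the stopping rule based on it, from progressive disease, toxicity that prevents continuation, and death. The sentence in 6.2.3.2 enters none of these.

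**The case against.** The strongest reply is that the sentence works at the level of a single assessment. It sits inside the definition of partial response, beside a complete-response condition that is plainly about classification. Objective status is recorded at each evaluation (6.2.2.2), and 6.2.8 speaks of weighing steroid changes before response is determined. On this reading, shrinkage seen on raised steroids simply earns no credit, which is conservative. Section 8 holds the population rule and does not mention steroids. Section 6.2.6 treats the patient with raised steroids as having stable disease, which is already a non-response. This reading is plausible and may be what was intended. It does not remove the problem, because 6.2.3.2 says evaluable, Section 8 uses that term for the denominator, and no section says how the patient is counted.

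A reader might go further and infer that deteriorating patients in general leave the denominator and that the rate is therefore inflated. The documents do not support that. Section 8 keeps neurologic progression as non-response, and 6.2.3.4 classes worsening disease as progression at any steroid dose. Nor is every steroid increase a sign of tumour worsening: Section 4.1.4 lists a short course of oral prednisone among treatments reported to help the lapatinib rash. A reader might also see a contradiction between 6.2.6 and the response rate, with the same patient a failure in one and missing from the other. That arises only if the literal reading of 6.2.3.2 is adopted first.

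It is also fair to say that the response rate is secondary, with no target, test or power, and that Section 8 plans no formal comparison with 20%.

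**Conclusion.** The point holds as an ambiguity with a known direction. Under the literal reading, patients with raised steroids and no progression can be dropped from the response rate, and the rate can be inflated. Under the assessment-level reading there is no bias. The text does not decide between the two, which leaves the denominator open to choice once results are known.

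From 20% at N = 50, the increase is 0.4 points for one such patient, 2.2 for five and 5.0 for ten; it is larger if fewer patients have measurable disease. These sizes assume that none of the patients left out has a response at another assessment that meets the steroid condition. They also rest on assumed counts, so that inflation will occur, or by how much, is not established. The effect is confined to the secondary response rate and the analyses that use responder status.

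**What to change.** Two changes of wording:

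- In 6.2.3.2, replace the evaluability sentence with one saying that a partial response can be credited only at an assessment that meets the steroid condition.
- In Section 8, Secondary Efficacy Analysis, add that a patient with measurable disease whose steroid dose has risen remains in the denominator, and counts as a non-responder unless a complete or partial response is met at an assessment that satisfies the steroid condition.

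If the assessment-level reading was intended, this only writes it down. The steroid data are already recorded in each course (6.2.8). Accrual is closed (Section 2.3), but the change concerns analysis only and needs no new procedures. The cost is that the reported response rate may be slightly lower than under the literal reading.
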